Carbidopa-levodopa in Neovascular AMD

Study design: Prospective, open label, two-parallel group

PI: [name], PhD, PC

Unique Protocol ID: 0001

Protocol Version 4

Date: June 24, 2017

IND Number: 132078

ClinicalTrials.gov Identifier: NCT 03022318

Study 001: Short term effects of carbidopa-levodopa in Neovascular AMD

Synopsis

In 2008, [name] identified a receptor, GPR 143, on the surface of RPE cells and discovered that L-DOPA was the natural ligand or stimulator of GPR143. He showed that treatment of RPE cells with exogenous L-DOPA resulted in the release of additional PEDF. In subsequent work his group also showed that L-DOPA stimulation of PEDF in RPE cells was also associated with a decrease in VEGF. Thus, [name] hypothesized that exogenous L-DOPA may prevent the onset of AMD or progression to wet AMD.

In 2015, [name] and his associates published a paper that showed that patients, who had been treated with L-DOPA, had a delay in the onset of AMD by 8 years, compared to patients who had not been treated with L-DOPA. In addition, those who had AMD and went on to develop wet AMD, did so 5 years later than those with no history of L-DOPA treatment. L-DOPA is an intermediate in the pigmentation pathway. [name] et al suggested that the reason darkly pigmented races do not get AMD nearly as frequently as lighter pigmented races, is that they produce more pigment, and thus more L-DOPA to stimulate GPR143 on RPE cells. According to this hypothesis, the stimulated RPE cells release PEDF and decrease VEGF, which together are responsible for the protective effect.

Since there are no established animal models for AMD, and L-DOPA has a good safety profile in healthy volunteers and patients with Parkinson's disease, we initiated a prospective trial to show efficacy in patients with neovascular AMD. This trial is in patients who have not had intraocular anti-VEGF injections. This trial will also evaluate the safety and tolerability of L-DOPA, in this population of patients with Wet AMD. The patients will be made aware of potential side effects of L-DOPA.

Design: Prospective, two parallel group, open label

Objectives

1 To determine whether L-DOPA-carbidopa supplementation can improve or stabilize the anatomic findings on OCT, within 30 days, in patients with choroidal neovascular AMD.

2 To determine whether L-DOPA-carbidopa supplementation can improve or stabilize visual function within 30 days, in patients with choroidal neovascular AMD, by testing ETDRS visual acuity.

3 To evaluate the relative benefits of carbidopa-levodopa 25-100 mg, one tablet once daily hs and one tablet TID

4 To determine whether L-DOPA-carbidopa supplementation is well tolerated in our target group of patients with wet AMD in one eye.

Inclusion criteria

- 1 A diagnosis of AMD with choroidal neovascularization (CNV) in one eye.
- 2 Not previously treated with anti-VEGF injections.
- 3 Normal or dry AMD of any grade in the second eye.
- 4 Age 50-85 years.
- 5 Willingness to maintain AREDS vitamin supplements throughout the study, or remain off these supplements for the duration of the study, if not taking them prior to the study;

Treatments:

Patients receive either open label, carbidopa 25-100 mg, one tablet once daily hs for one month or one tablet dosed three times daily, in the morning, with supper and hs for one month (100 or 300 mg of levodopa daily). This is the equivalent of very low to low doses of carbidopa-levodopa in patients with Parkinson's disease.

Each patient will be reevaluated at weekly (5-8 day) intervals.

Duration: up to 32 days of treatment. This study will end with the first anti-VEGF injection, or after Visit 5, whichever occurs first. At the end of the study, patients will be eligible to enter Study 002.

Measurements and Activities:

- 1 Ophthalmic history and comprehensive eye examination; including visual acuity, with best correction, using an EDTRS chart, in both eyes prior to randomization, and ophthalmoscopic eye examination, and OCT;
- 2 Repeat assessment of visual acuity using an EDTRS chart, ophthalmoscopic eye examination, and OCT at weekly visits;

Criteria for anti-VEGF injections

This will be based on: weekly evaluation of ETDRS visual acuity (decrease of 5 letters from previous visit); increased macular thickness (compared to normal and previous visit as measured by OCT); new blood (hemorrhage on direct retinal examination; or subjective decrease in vision. If any of these criteria are met, or if, in the opinion of the Ophthalmologist, or the patient's Retina Specialist, the patient requires anti-VEGF therapy, the patient will have an anti-VEGF intraocular injection, by his or her Retina Specialist. If none of these criteria are met at visits 2, 3 or 4, with patient agreement, anti-VEGF injection will not be done, and the patient will be reevaluated in 1 week.

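### Every patient takes levodopa and no benchmark is named for Objectives 1 and 2, so the stated aim of showing efficacy claims more than the design supports

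*Protocol*

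**What the plan says.** The Synopsis gives the purpose: "we initiated a prospective trial to show efficacy in patients with neovascular AMD". Objective 1 is "To determine whether L-DOPA-carbidopa supplementation can improve or stabilize the anatomic findings on OCT, within 30 days, in patients with choroidal neovascular AMD". Objective 2 asks whether the supplement "can improve or stabilize visual function within 30 days", measured by ETDRS acuity.

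The Design line describes two parallel open-label groups. Under Treatments, "Patients receive either open label, carbidopa 25-100 mg, one tablet once daily hs for one month or one tablet dosed three times daily", which the protocol converts to "100 or 300 mg of levodopa daily". Both groups therefore receive the study drug.

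The one objective that sets the groups against each other is Objective 3: "To evaluate the relative benefits of carbidopa-levodopa 25-100 mg, one tablet once daily hs and one tablet TID". The Inclusion criteria (item 3) require of the fellow eye: "Normal or dry AMD of any grade in the second eye".

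**The concern.** Objectives 1 and 2 ask a causal question: does the drug improve or stabilise the eye? Answering it needs some account of what the eye would have done over the same month without the drug. The protocol supplies none, neither a concurrent group nor an external figure.

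The word for stabilisation is the most exposed. A flat course under an inactive drug would meet it. The error can also run the other way, because an active drug working against a declining course can look like no change. If the wording stands, a within-arm result could be reported as efficacy when the trial has not tested that. Patients who finish are eligible for a follow-on study (Study 002), so the conclusion drawn here may carry forward.

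**Working it through.** The protocol states no sample size, effect size, SD or response rate, so there is no figure to reproduce. The check is whether the quantity that Objectives 1 and 2 ask about can be recovered from the two arms.

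**Inputs from the protocol**
- Arms: 100 mg and 300 mg of levodopa daily (Treatments). There is no zero-dose arm.
- Outcomes: OCT findings and ETDRS letters within 30 days (Objectives 1 and 2).
- Between-group contrast: once daily against three times daily (Objective 3).

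**Step 1: what the arms estimate.** Let m be the mean 30-day change without levodopa, and e100 and e300 the effects of the two regimens against no levodopa.
- Once-daily arm mean = m + e100
- Three-times-daily arm mean = m + e300
- Difference = (m + e300) - (m + e100) = e300 - e100

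That is two equations in three unknowns. Adding any constant t to m and subtracting t from both effects leaves both arm means unchanged. Only e300 - e100 is identified, and more patients do not alter this.

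**Step 2: equal effects.** The letter values are assumed, for illustration only.

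| m | e100 | e300 | Once-daily mean | Three-times-daily mean | Difference |
|---|---|---|---|---|---|
| 0 | 0 | 0 | 0 + 0 = 0 | 0 + 0 = 0 | 0 |
| -3 | +3 | +3 | -3 + 3 = 0 | -3 + 3 = 0 | 0 |
| +2 | -2 | -2 | +2 - 2 = 0 | +2 - 2 = 0 | 0 |

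An inactive drug, a helpful one and a harmful one give the same data, and all three would read as stabilised.

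**Step 3: apparent improvement.** An observed within-arm gain of +2 letters fits m = +2 with effect 0 (2 + 0 = 2). It fits m = -3 with effect +5 equally well (-3 + 5 = 2).

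**Step 4: regimens that differ.** Suppose the arm means are 0 and +2, so the difference is +2.
- m = 0 gives e100 = 0 - 0 = 0 and e300 = 2 - 0 = +2.
- m = -3 gives e100 = 0 + 3 = +3 and e300 = 2 + 3 = +5.
- m = +2 gives e100 = 0 - 2 = -2 and e300 = 2 - 2 = 0.

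A real difference shows that the regimen matters, which is indirect evidence of activity. It does not give the size or the sign of either regimen's effect against none.

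**Step 5: could anything else in the protocol stand in for m?**
- The fellow eye is normal or has dry AMD, so its course is not that of an untreated neovascular eye, and it is exposed to the same oral drug. The protocol does not offer it as a control.
- The treated-versus-untreated data cited in the Synopsis concern timing of disease: AMD starting 8 years later and wet AMD 5 years later. They give no 30-day change in OCT findings or letters.

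Neither supplies m.

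**The case against.** The strongest reply is that an early, open-label study of two regimens without an untreated group is a legitimate design. The study title speaks only of short-term effects, and the protocol states no hypothesis test or power claim against no treatment. The objectives can also be read as change from baseline, which the design can report. Much of this stands: it makes the point one of wording, with no extra arm needed. It does not save the text. The Synopsis speaks of showing efficacy, and Objectives 1 and 2 ask what the supplement can do, which attributes the change to the drug. If description is meant, saying so costs nothing.

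A second reply is that the analysis plan, which is not at hand, may name an external benchmark. It may, and the fix allows for that. It cannot create a concurrent group, because the arms are fixed in the protocol.

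A reader might go further in two ways that the document does not support.
- One might say that the trial has no comparator at all. That is untrue for Objective 3, where each regimen is the other's comparator.
- One might infer that stabilisation will be overstated because worsening patients leave: "This study will end with the first anti-VEGF injection, or after Visit 5, whichever occurs first", and loss of letters or increased thickness can trigger that injection. This would follow only from a summary restricted to patients who reach Visit 5. The protocol specifies no such analysis, and the handling of injected patients is commonly left to the analysis plan. It also gives no variability figures from which to size the effect. The point here does not rest on it.

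**Conclusion.** The concern holds for the stated aim in the Synopsis and for Objectives 1 and 2. As designed, the trial cannot estimate the effect of levodopa against no treatment. This is a failure of identification, so it has no size in letters or microns and does not shrink with more patients. The letter values in the working are assumed; the conclusion needs only that both arms receive levodopa and that no external benchmark is named.

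The design can describe change within each regimen and tolerability (Objective 4), and it can compare the two regimens (Objective 3). A causal reading of that comparison assumes randomised allocation, which the protocol mentions only as a time point under Measurements and Activities. A null difference would not separate two active regimens from two inactive ones.

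This does not mean that no efficacy statement could ever be made from within-arm data. A comparison with an external benchmark specified in advance would be possible, and as strong as that benchmark.

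**What to change.** 1. Reword Objectives 1 and 2, for example: *To describe the change from baseline in OCT findings (Objective 1) and ETDRS acuity (Objective 2) over up to 30 days within each regimen.*

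2. In the Synopsis, replace the efficacy aim with an exploratory one and add: *The design has no concurrent group without L-DOPA and does not estimate the effect of L-DOPA against no treatment. No efficacy claim will rest on within-arm change or a stabilisation rate unless it is compared with an external benchmark specified in advance. A null difference between regimens is not evidence for or against activity.*

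The cost is a weaker stated claim. Arms, doses, visits and the injection rule are unchanged.

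### The acuity criterion for anti-VEGF injection has no baseline reference, so a gradual measured loss of 2 to 4 letters per visit never meets it

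*Protocol*

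**What the plan says.** The protocol's section Criteria for anti-VEGF injections lists four findings, any one of which leads to injection:

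- acuity: "weekly evaluation of ETDRS visual acuity (decrease of 5 letters from previous visit";
- OCT: "increased macular thickness (compared to normal and previous visit as measured by OCT", with no size threshold;
- new blood on retinal examination;
- a subjective decrease in vision.

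A fifth route is clinical opinion: "or if, in the opinion of the Ophthalmologist, or the patient's Retina Specialist, the patient requires anti-VEGF therapy". Waiting is allowed as follows: "If none of these criteria are met at visits 2, 3 or 4, with patient agreement, anti-VEGF injection will not be done".

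Under Duration, "This study will end with the first anti-VEGF injection, or after Visit 5, whichever occurs first". Measurements and Activities, item 1, already calls for a baseline score ("including visual acuity, with best correction, using an EDTRS chart, in both eyes prior to randomization"), and item 2 repeats acuity weekly. Inclusion criteria, items 1 and 2, bring in eyes with CNV that were "Not previously treated with anti-VEGF injections".

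Nothing in the protocol compares a later acuity score with the pre-randomization score. That score serves as the reference only at Visit 2, where it happens to be the previous visit.

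**The concern.** The acuity criterion is the one part of the rule that works without judgement. Because it resets at each visit, it responds to a sudden fall but not to the sum of small ones. An eye can be more than 5 letters below its starting score and still not meet a criterion whose threshold is 5 letters.

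The OCT criterion does not supply the missing baseline, since it too looks back to the previous visit. It is also silent in an eye whose thickness is falling or not above normal. Falling thickness is a result the trial hopes to see: Objective 1 is "To determine whether L-DOPA-carbidopa supplementation can improve or stabilize the anatomic findings on OCT, within 30 days". If acuity slips slowly in such an eye, what remains is new blood, the patient's own report, or clinical opinion with no numeric prompt. At stake is delayed rescue in an untreated CNV eye, over a treatment period of up to 32 days.

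**Working it through.** The protocol gives no figure to reproduce, so the check has three steps.

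**1. Arithmetic on the rule.** Inputs: 5-letter threshold against the previous visit; injection may be withheld at Visits 2, 3 and 4, which is three intervals after Visit 1. The protocol does not define Visit 1; it is taken here as the pre-randomization visit. Cumulative loss = letters per visit × intervals.

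| Measured loss per visit | Visit 2 | Visit 3 | Visit 4 | Meets criterion as written | First meets a 5-letter loss from Visit 1 |
|---|---|---|---|---|---|
| 1 | 1 | 2 | 3 | never | never |
| 2 | 2 | 4 | 6 | never | Visit 4 |
| 3 | 3 | 6 | 9 | never | Visit 3 |
| 4 | 4 | 8 | 12 | never | Visit 3 |

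**2. Allowing for test noise, acuity criterion alone.** Real scores vary, and noise sometimes produces a 5-letter drop between visits. The documents give no test SD or rate of loss, so everything in this step is assumed: independent normal error with SD 2, 3 or 4 letters, scores rounded to whole letters, a fall of 5 read as 5 or more, 400,000 simulated eyes per setting. Entries are the percentage meeting the criterion by Visit 4: as written → with Visit 1 added (difference in points).

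| True loss per week | SD 2 | SD 3 | SD 4 |
|---|---|---|---|
| 0 (stable) | 16.7 → 21.5 (4.8) | 40.8 → 46.6 (5.8) | 57.4 → 61.9 (4.5) |
| 1 letter | 31.4 → 48.9 (17.5) | 55.6 → 65.9 (10.3) | 68.8 → 75.0 (6.2) |
| 2 letters | 51.9 → 81.2 (29.3) | 70.6 → 83.4 (12.8) | 79.3 → 85.9 (6.6) |
| 3 letters | 74.3 → 97.1 (22.8) | 83.8 → 94.4 (10.6) | 87.8 → 93.5 (5.7) |
| 4 letters | 91.3 → 99.8 (8.5) | 93.0 → 98.8 (5.8) | 93.8 → 97.6 (3.8) |

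At these SDs the gain is largest at 2 letters per week, so that row should not be quoted alone. Nor is SD 2 a limit: at SD 1 and 2 letters per week the figures are 12.3 → 86.8, a difference of 74.5 points.

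**3. Adding the OCT trigger.** Assume OCT fires on any rise over the previous reading in an above-normal macula, with OCT error independent of acuity error. If true thickness is stable, the chance of no rise across four readings is 1/4! = 1/24 = 4.17%. If thickness falls by one OCT-error SD per week, simulation gives 37.0%. Whole-rule gain = acuity gain × that share. For a true loss of 2 letters per week at SD 2/3/4:

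- stable thickness: 29.3 × 0.0417 = 1.2; 12.8 × 0.0417 = 0.5; 6.6 × 0.0417 = 0.3 points;
- thickness falling 1 SD per week: 29.3 × 0.370 = 10.8; 12.8 × 0.370 = 4.7; 6.6 × 0.370 = 2.4 points;
- macula not above normal, so OCT never fires: the full 29.3, 12.8 and 6.6 points.

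The cost in truly stable eyes shrinks in the same way: with stable thickness, 4.8 × 0.0417 = 0.2 points at SD 2. No credit is given here to blood, symptoms, clinical opinion or patient refusal, all of which would lower the figures further.

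**The case against.** The strongest reply is that the rule must be judged as a whole. Four other routes lead to injection, the OCT route has no minimum size, either clinician's opinion is enough, and waiting needs the patient's agreement. Acuity is recorded before randomization and weekly, so a clinician can see a cumulative loss and act on it. If the OCT wording is read so that being above normal is sufficient by itself, every above-normal macula triggers at once and the gap there is zero. All of this stands. It is why the point concerns one criterion and does not say that the rule as a whole fails.

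The reply does not justify the further claim that the other routes would catch most slow decliners. If they acted independently at each of Visits 2 to 4 with chance q, the share caught would be 1 − (1 − q)³, which exceeds one half only when q is above about 0.206. The protocol offers no value of q.

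A reader might also infer the opposite extreme: that the protocol lets eyes lose 12 letters untreated. The documents do not support that. Twelve letters is the largest loss that steps of under 5 letters can accumulate by Visit 4 without meeting this one criterion, and each other route remains open. At an assumed SD of 2/3/4, an eye that is 12 letters down at Visit 4 with the acuity criterion still unmet occurs in 0.03/0.04/0.03% of eyes at a true loss of 2 letters per week and 0.39/0.11/0.05% at 4 per week.

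Finally, the amendment is a trade-off. The criterion as written already fires in 17 to 57% of truly stable eyes under these assumptions, and at SD 4 the gain in declining eyes (3.8 to 6.6 points) is close to the cost in stable ones (4.5 points). A sponsor could defend leaving slow drift to clinicians, but the protocol does not say that this was the intention.

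**Conclusion.** The point holds for the acuity criterion. It has no baseline reference, and measured losses of 2 to 4 letters per visit, totalling 6 to 12 letters by Visit 4, never meet it. This follows from the text, given only that the pre-randomization visit is Visit 1.

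The size of the effect is illustrative. For acuity alone, at an assumed SD of 2 to 4 letters, the baseline reference adds about 4 to 29 points of triggers in eyes truly losing 1 to 4 letters per week. For the whole rule the gain is smaller. It depends on how the OCT criterion is read, on the course of macular thickness and on clinical judgement, none of which the protocol quantifies. The gap matters most in eyes whose thickness is falling or not above normal. This is an inexpensive improvement to consider, not evidence that the rescue rule as a whole is unsafe.

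**What to change.** Amend the acuity criterion to a loss of 5 or more letters relative to either the preceding visit or the pre-randomization score, and state that the pre-randomization visit is Visit 1. No new measurement is needed.

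The cost is about 5/6/5 points more acuity triggers by Visit 4 in truly stable eyes (assumed SD 2/3/4). Each leads to an injection and ends that patient's participation. With the other triggers counted, the added cost is smaller.

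The baseline comparison should be added to the previous-visit comparison, not replace it. A Visit 1 reference alone would lower triggers in stable eyes to 13/30/41%. But it would miss a sudden fall after a gain and, at SD 4 and a true loss of 2 letters per week, catch fewer declining eyes (74% against 79% as written).
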